- Electrocardiographic parameters, in particular specific conduction alterations or arrhythmias and QTc value according to Fridericia, collected at baseline, after 15 and after 30 days from start;
- Patient comorbidity, understood as concomitant disease at the start of treatment with CDK4/6i ascertained by the physician and classified in macro-areas (e.g. cardiological, respiratory, metabolic, infectious, chronic diseases such as diabetes mellitus type 2);
- Concomitant therapies, initiated and ongoing before the start of treatment with CDK4/6i, reported as drug classes (e.g. steroid therapy, antibiotic therapy, proton pump inhibitors);
- Blood glucose and body mass index at baseline of CDK4/6i treatment.

(3) Medical imaging sub-study

Objectives and endpoints of the sub-study

Primary objective:

- To build a model able to predict prognosis of HR+/HER2- aBC patients treated with first-line ET+CDK4/6i using radiomics features extracted from baseline radiological images;
- To build a model able to predict prognosis of HR+/HER2- aBC patients treated with first-line ET+CDK4/6i using radiomics features extracted from baseline radiological images;
- To combine radiomics and pathomics features with clinical data to build a model able to predict prognosis of HR+/HER2- aBC patients treated with first-line ET+CDK4/6i;

Secondary objectives:

- To combine radiomics features with clinical data, pathomics, genomics and transcriptomics features to build a model able to predict prognosis of HR+/HER2- aBC patients treated with first-line ET+CDK4/6i;
- To build a model able to classificate HR+/HER2- aBC patients treated with first-line ET+CDK4/6i in early and late progressors using radiomics features extracted from baseline radiological images;
- To build a model able to predict prognosis of HR+/HER2- aBC patients treated with first-line ET+CDK4/6i using baseline radiomics features and early radiomics modifications detected from first on-treatment radiological evaluation;
- To build a model able to predict molecular characteristics, such as *PIK3CA* and *ESR1* mutational status, of HR+/HER2- aBC patients treated with first-line ET+CDK4/6i using radiomics features extracted from baseline radiological images;
- To build a model able to predict molecular characteristics, such as *PIK3CA* and *ESR1* mutational status, of HR+/HER2- aBC patients treated with first-line ET+CDK4/6i using radiomics features extracted from digitalized HE slides;

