This sub-study encompasses the collection of tumor samples of patients enrolled in the PALMARES-2 RWD sub-study. At least one formalin-fixed paraffin-embedded tumor block will be collected from diagnostic biopsy or surgical specimens, performed for diagnostic purposes as per clinical practice. Both tumor samples from primary tumor and from metastatic sites underwent biopsy will be collected, if available. If more than one metastatic biopsy has been performed during the course of patient's disease, all the non-stained slides and/or tumor blocks should be collected, if available. If a patient did not undergo neoadjuvant treatment, diagnostic biopsy of the breast or surgical tumor slide could be collected equivalently; otherwise, the diagnostic biopsy performed before treatment initiation should be taken.

(5) Second and further lines sub-study

Objectives and endpoints of the sub-study

Primary objective:

To build a model based on clinical, radiomics and pathomics data to select the best treatment option in terms of OS in HR+/HER2- aBC patients progressing after first-line ET+CDK4/6i.

Secondary objectives:

- To build a model based on clinical data to select the best treatment option in terms of OS in HR+/HER2- aBC patients progressing after first-line ET+CDK4/6i.
- To build a model based on clinical, radiomics, pathomics, genomics and transcriptomics data to select the best treatment option in terms of OS in HR+/HER2- aBC patients progressing after firstline ET+CDK4/6i.
- To assess the efficacy in terms of rwPFS and OS of second and subsequent line of therapy in a realworld setting of HR+/HER2- aBC patients progressing after first-line ET+CDK4/6i.

Study Population

The same inclusion and exclusion criteria adopted for the RWD sub-study will be applied for the present sub-study, for the only exception of the following inclusion criteria: Version 1.1, 01Aug2024

- Clinical, biochemical or radiological progression on CDK4/6i+ET first-line treatment
- Second-line therapy start after CDK4/6i+ET progression
- Data availability about at least one of the subsequent lines, including at least the treatment line of therapy, treatment start date, treatment progression date or last follow up, type of treatment and drug used.

Data collection

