Clinical real world data will be collected by centers in ad hoc document in .xlsx format. At pre-specified data cut-off (see sections below), data collected will be shared with the Sponsor for data analyses. Investigators at study centers could be required to modify data in case of data inconsistencies encountered during data analyses.

All consecutive HR+ HER2- aBC patients treated with first-line ET plus CDK 4/6i as per clinical practice in the time interval between January 2017 and December 2030 will be enrolled retrospectively and prospectively. Data will be collected in a continuous manner and will be shared with the Sponsor center on an annual basis, at pre-specified data cut-offs. Data cut-offs will occur annually, at certain cutoffs falling on 1st January of each year. Taking into account the time interval and the centers involved, approximately 2000 patients will be included at the first data cut-off of 1st January 2024. Those patients who have already concluded the treatment at the time of study inclusion will be evaluated for clinical outcomes (i.e. PFS, OS) and biological parameters of interest will be retrospectively collected. Patients who are still receiving ET plus CDK4/6i at the time of inclusion in the study will be evaluated for the same variables until the end of the study. At the time of data collection and analysis, these patients will be censored for the events of interest (e.g. progression, death) if these events have not occurred yet.

[figure not shown]

Figure 2. PALMARES-2 study expected timeline and enrollment. EC: ethical committee; pts: patients.

Medical images collection and sharing

The medical images, collected within the timeframe specified in the appropriate section (see section "Medical images sub-study"), will be collected locally in the individual centers, pseudonymised and uploaded to an ad hoc secure sharepoint. A folder will be set up for each individual center participating in this sub-study, so that only the center uploading the images and the Sponsor center itself will be able to access them.

Tumor samples collection, storage and shipment

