A team of four radiologists with experience on CT scan/PET images segmentation will identify the Volume Of Interest (VOI) through a semi-automated 3D segmentation process performed with Syngo.via software. An ad hoc designed segmentation protocol will be applied to homogenize the choice of CT/PET sequence on which to perform segmentation and the choice of the lesion to be segmented. Peritumoral area will be obtained through automated augmentation techniques (+5 mm, +10 and +15 mm); if the peritumoral area obtained crosses blood vessels, gas, bone, bile duct, or exceeded the organ edge, the contour will be manually modified to exclude this area. After image pre-processing through different techniques (e.g., gray discretization, intensity normalization, and voxel resampling), radiomic features will be extracted from VOIs and peritumoral areas using the PyRadiomics library in Python. In order to prevent signature overfitting, dimensionality of features is reduced before signature construction, firstly excluding features with high intraclass correlation coefficient and significantly different between the two outcome groups as assessed by one-way analysis of variance (ANOVA). Least absolute shrinkage and selection operator (LASSO) regression and/or Maximum Relevance Minimum Redundancy (MRMR) will be then used for the selection of features that will be included in the final model. The cohort will be split in a training (80%) and testing cohort (20%). Different standard classifiers, such as Random Forest, Multilayer perceptron, Logistic

Regression, Support Vector Machine, CatBoost, AdaBoost, XGBoost, will be trained and evaluated for this task. 91,92

Pathomics Methodology

Pathology slides will be digitalized with Leica Scanscope AT2 and stored as ".svs" files to obtain Whole Slide Images (WSIs). Hematoxilin and Eosin (HE) slides will be digitalized for pathomics purposes. WSIs will be analysed through Slideflow, a Python package that provides a unified Application Programming Interface for building and testing models for histopathology. After color normalization procedures, quantitative pathomics features will be extracted. Model creation and performance evaluation will follow the same methodology discussed in the "Radiomics" workflow. 93

Multimodal integration

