We will use several architectures, including logistic regression, classification and regression trees, random forest, multi-layer perceptron, gradient boosted trees (XGBoost), gradient boosting machines (LightGBM) and attentive tabular networks TabNet and we will compare their performance to heuristically decide on the best model choice for follow-up experiments. Our modelling experiments will include different combinations of input embeddings, with concatenation of each data stream permutation to produce fusion embeddings and train models using single-modality or multi-modality of input combinations. All models will be trained multiple times with multiple different data splits to repeat the experiments and compute average metrics and SDs. All defined models will be trained and tested to evaluate the advantage of multimodal predictive systems, as compared to single modality ones for the pre-established classification prediction. To assess model performance, different metrics will be used, including AUC, Sensitivity and Specificity, which will be calculated on the training set through 10-fold cross-validation and on the test set, which will be obtained by randomly splitting the entire cohort in a 80:20 way. The hyperparameter combinations of individual models, such as maximum depth of the trees, number of estimators and learning rate, will be selected within each training loop using a fivefold cross-validated grid search on the training set.^{94,95}

Since these complex models are considered as "black boxes", since they make decisions without clear reasoning, explainability techniques will be adopted to provide insights into how models make predictions, guaranteeing human interpretability. In particular, SHapley Additive exPlanations (SHAP) techniques will be used for both global and local explanations. ⁹⁶

Biological analyses methodology

Genomic analyses

A next generation sequencing (NGS) panel (Oncomine Comprehensive Assay Plus) will be used to perform analysis of various single-gene variants, such as single nucleotide variations (SNVs), indels, fusions, splice Version 1.1, 01Aug2024

Pag. 26 di 32

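### The prognosis and post-progression OS models target censored outcomes, but the protocol commits them to two-class methods with no time horizon and no step that handles censoring

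*Protocol*

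**What the plan says.** **Targets.** The first primary objective of the Medical imaging sub-study (section 3) begins "To build a model able to predict prognosis of HR+/HER2- aBC patients treated with first-line ET+CDK4/6i". A further primary objective is "To combine radiomics and pathomics features with clinical data to build a model able to predict prognosis of HR+/HER2- aBC patients". Neither names an endpoint. The primary objective of the Second and further lines sub-study (section 5) does: "To build a model based on clinical, radiomics and pathomics data to select the best treatment option in terms of OS". A secondary imaging objective sorts patients "in early and late progressors using radiomics features extracted from baseline radiological images", with no cut-point in months.

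**Censoring.** Under Clinical data collection and management, patients still on treatment with no event at a cut-off are handled as follows: "these patients will be censored for the events of interest".

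**Methods.** Radiomics Methodology screens features by whether they are "significantly different between the two outcome groups as assessed by one-way analysis of variance (ANOVA"), and then trains "Different standard classifiers, such as Random Forest, Multilayer perceptron, Logistic" regression and others. Pathomics Methodology adopts the same model building and evaluation. Multimodal integration describes the task as a classification fixed in advance and says: "To assess model performance, different metrics will be used, including AUC, Sensitivity and Specificity". Statistical methods takes AUC from caret and pROC and compares models with DeLong's test. The only related data rule, in the same section, excludes patients whose outcome is missing.

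**The concern.** A two-group ANOVA, a classifier, and sensitivity, specificity and pROC's AUC all need a known yes/no outcome for each patient. A patient censored at 14 months has no known 24-month status. The protocol commits to the two-class framework for its prognosis and OS models but supplies none of what would make it valid for censored data: a horizon, a labelling rule, a survival learner, a C-index, a time-dependent AUC or censoring weights. Kaplan-Meier and Cox methods appear in the general statistics but are not linked to these models. The early/late progressor objective is separate and secondary, so it does not supply the missing label.

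Two simple ways to force a label are to exclude patients of unknown status or to count them as event-free. The missing-outcome rule points towards the first. Excluding them overstates risk, because patients with an early event stay in while event-free patients with short follow-up leave. Counting them as event-free understates risk. The protocol wants individual prognosis in order to consider escalating or de-escalating treatment, so an error in absolute risk matters.

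**Working it through.** **The plan's own figures.** The modelling sections give no sample size, horizon or performance target to reproduce. The one relevant design figure is the RWD sub-study target of 977 OS events in 3258 patients: 977/3258 = 30.0%, which leaves 70% without an OS event.

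**Inputs from the protocol.**
- Minimum follow-up of 3 months (RWD sub-study exclusion criteria).
- Treatment starts from January 2017 and first cut-off 1 January 2024 (Clinical data collection and management), so at most 84 months. Study duration gives January 2016 as the start; 2017 is used here.
- Median PFS 23.6 and 32.3 months, median OS 48.7 and 58.3 months (background, first-line HER2-low versus HER2-0 analysis).

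**Assumptions.** Follow-up C is uniform on 3 to 84 months, event times are exponential, and censoring is purely administrative.

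**Formulas**, with rate λ = ln 2 / median and horizon τ:
- true risk R = 1 − exp(−λτ)
- unknown status U = P(C < τ and T > C) = [exp(−3λ) − exp(−λτ)] / (81λ)
- known event-free K = exp(−λτ) × (84 − τ)/81
- observed events E = 1 − U − K
- risk if unknowns are excluded = E/(E + K); risk if they count as event-free = E.

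**Example: median 23.6, τ = 24.** λ = 0.02937.
- U = (0.9157 − 0.4942)/(81 × 0.02937) = 0.177
- K = 0.4942 × 60/81 = 0.366
- E = 1 − 0.177 − 0.366 = 0.457
- R = 0.506; excluded 0.457/0.823 = 0.555; event-free 0.457.

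| Median PFS | τ (months) | Unknown | True risk | Excluded | Event-free |
|---|---|---|---|---|---|
| 23.6 | 6 | 3.2% | 16.2% | 16.6% | 16.0% |
| 23.6 | 24 | 17.7% | 50.6% | 55.5% | 45.7% |
| 23.6 | 36 | 23.9% | 65.3% | 72.9% | 55.5% |
| 32.3 | 6 | 3.4% | 12.1% | 12.4% | 12.0% |
| 32.3 | 24 | 19.6% | 40.3% | 45.0% | 36.2% |
| 32.3 | 36 | 27.4% | 53.8% | 62.3% | 45.3% |

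If OS from first-line start were the endpoint, the same formulas leave 36-month status unknown for 31-33%. Risk shifts by about +8 points (excluded) or −6 to −7 points (event-free). The protocol gives no median for OS after progression under current first-line treatment, so the later-lines model cannot be sized in this way.

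**Later cut-offs.** For the same patients one year on, C runs from 15 to 96 months, and replacing 3 by 15 in U gives 6.3% and 7.3% unknown at 24 months. Two years on, C starts at 27 months and the figure is zero. Recently enrolled patients would still be affected at each cut-off.

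**Discrimination.** This needs a simulation: 400,000 patients, one score with an assumed log hazard ratio of 0.7 per SD, same follow-up. Results for median PFS 23.6 months:

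| τ (months) | True AUC | Event-free | Excluded | Censoring weights |
|---|---|---|---|---|
| 24 | 0.740 | 0.727 | 0.742 | 0.739 |
| 36 | 0.760 | 0.730 | 0.766 | 0.759 |

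The weights also recover the 24-month risk (0.505 against 0.505). At 36 months, counting censored patients as event-free lowers specificity from 0.739 to 0.681. Larger AUC shifts arise only if the score is also assumed to drift with calendar date of treatment start: at 36 months, down 0.06-0.09 (event-free) or up 0.03-0.05 (excluded).

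**The case against.** The strongest reply is that the protocol never says censored patients will be excluded or counted as event-free. A reader might infer that it does, but the text is silent, and the endpoint, horizon and labelling rule could be set in a SAP that is not available here. The lists of metrics and classifiers are open-ended. This stands as far as it goes: the bias is conditional. It does not remove the point, because the two-group screen, the classification task and the ROC tools are choices the protocol has made, and they do not fit the censored target it also names.

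Second, a binary classifier is not doomed. Restricting by start date to patients whose potential follow-up reaches the horizon, with or without an event, is unbiased under administrative censoring, and so are censoring weights. This stands, and both belong in the fix.

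Third, size depends on choices outside the protocol. The background puts early progression at roughly 10-15% of patients, which suggests a short horizon, and at 6 months the risk bias is within about 0.5 points. No passage ties model building to the 2024 cut-off. Both stand.

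A reader might also infer that the models would learn length of follow-up instead of biology. That would need baseline features that vary with calendar time, which the documents do not show, or a label of having progressed by the cut-off, which the protocol does not define. Nor are classifiers wrong throughout: they and plain AUC suit the PIK3CA/ESR1 and PAM50 objectives, which involve no censoring.

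**Conclusion.** The point holds in a limited form. For the prognosis models and the later-lines OS model, the stated methods do not fit the target: the outcomes are censored, and the screen, learners and metrics presuppose a known two-class label, with no horizon and no censoring-aware step. The early/late progressor model shares the problem because its cut-point is undefined.

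The harm is conditional on excluding patients of unknown status or counting them as event-free. Under even accrual from January 2017, a January 2024 cut-off and exponential PFS with the protocol's medians, the error in absolute risk is about 4-5 points at 24 months and 8-10 points at 36 months, in opposite directions for the two rules. It is negligible at 6 months and falls as follow-up matures. AUC moves by at most 0.03 unless features drift with calendar time. The change should be made, but the defect does not invalidate the sub-studies, and the documents do not show that any patient will in fact be mislabelled or dropped.

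**What to change.** For the prognosis and OS models, name the endpoint and adopt one of two routes:
- Survival learners on the same features (Cox-LASSO, random survival forest, gradient boosting with a Cox loss), with a Cox-based filter replacing the two-group ANOVA.
- A classifier at a fixed, stated horizon, with inverse-probability-of-censoring weights or restricted by start date to patients whose potential follow-up reaches that horizon, whether or not they had an event.

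Under either route, report the C-index, time-dependent AUC and calibration. Give the early/late progressor model a fixed horizon and the same weights. State that the missing-outcome exclusion does not apply to patients who are merely censored. Keep plain classifiers and AUC for the PIK3CA/ESR1 and PAM50 objectives.

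The cost is analysis code and somewhat less simple metrics; no new data are needed. The start-date restriction also gives up the most recently treated patients at each cut-off.

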we conducted a subanalysis on the PALMARES study cohort treated with first-line CDK4/6i plus ET. HER2 status was available for 428 patients in the study cohort. We found that patients with HR+/HER2-low aBC had significantly worse PFS (mPFS 23.6 months vs. 32.3 months; p=0.014) and OS (mOS: 48.7 vs 58.3 months; p=0.029) when compared to patients with HER2-0 aBC. Multivariable analysis confirmed an independent association between HER2-low status and worse PFS (aHR 1.42; 95% CI:1.07-1.89; p=0.016) and OS (aHR: 1.64; 95% CI: 1.08-2.48; p=0.02).⁴⁸ However, another large study conducted by Mouabbi J. et al investigated the prognostic role of HER2 status in 1649 HR+/HER2- aBC patients treated with ET in combination with different targeted therapies (CDK4/6i, everolimus or alpelisib). In the sub-cohort of 919 patients treated with CDK4/6i plus ET, there were no statistically significant differences between patients with HER2-low and HER2-0 aBC in terms of PFS (13.0 vs 11.6 months, p=0.273) and OS (32.4 vs 31.2 months, p=0.222).⁴⁹ The reported discrepancies among published studies, in addition to the increased value of the HER2-low status in the treatment of HR+/HER2- aBC, laid the foundations for further investigations on this potentially useful and easy-to-access biomarker.

To summarize, our previous preliminary results, together with available literature, demonstrated that some biomarkers already available in clinical practice could be potentially used to distinguish different prognostic classes of HR+/HER2- aBC patients treated with first-line ET+CDK4/6i. However, larger studies are necessary to confirm available results and finally implement in clinical practice novel treatment biomarkers.

Differences between the three CDK4/6i drugs in combination with ET and their impact on efficacy

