- To test the association between blood lymphocyte counts at baseline, or their precocious ontreatment modifications (T1: 2 weeks after treatment initiation, and T2: before fourth cycle initiation, approximately 12 weeks after treatment initiation) and rwPFS, TTNT-D, TTC-D and OS of HR+/HER2- patients treated with first-line ET plus CDK4/6i;
- To evaluate the association between peripheral blood crude cell counts, namely whole blood cells, neutrophils, monocytes and platelets, as evaluated at baseline and as precocious on-treatment modifications, and patient rwPFS, TTNT-D, TTC-D and OS;
- To evaluate the association between baseline composite parameters, such as the Neutrophil-to-Lymphocyte ratio (NLR), the platelet-to-lymphocyte ratio (PLR), the monocyte-to-lymphocyte ratio (MLR), or the Pan-Immune Inflammation Value (PIV), and patient PFS;
- To evaluate the association between precocious on-treatment modifications (i.e., 2 weeks and ∼12 weeks after treatment initiation) of NLR, PLR, MLR and PIV, and patient PFS;
- To evaluate the association between HER2 status (HER2-low vs. HER2-0; HER2 2+ with negative ISH vs. HER2 1+ vs. HER2-0) in the primary tumor and rwPFS, TTNT-D, TTC-D and OS;
- To evaluate the association between HER2 status (HER2-low vs. HER2-0; HER2 2+ with negative ISH vs. HER2 1+ vs. HER2-0) in one metastatic site (subjected to biopsy before CDK 4/6 inhibitor initiation), and rwPFS, TTNT-D, TTC-D and OS;
- To explore pattern of progression of HR+/HER2- aBC after ET plus CDK4/6i treatment;
- To test the effect on rwPFS, TTNT-D, TTC-D and OS of mastectomy in patients with *de novo* HR+/HER2- aBC.

Study Population

Inclusion criteria:

- Pre- and Post-menopausal patient (woman OR man)
- Age≥18 years
- Diagnosis of aBC. HR+/HER2- aBC, as defined as at least 1% estrogen receptor (ER) and/or progesterone receptor (PgR) positivity at IHC. HER2 negativity is defined on the basis of an IHC score of 0, 1+, or 2+ with absence of gene amplification at in situ hybridization (ISH) analyses.
- Have received or are candidate to receive treatment with palbociclib, ribociclib or abemaciclib in combination with endocrine therapy as first-line treatment for HR+/HER2- aBC.

Exclusion criteria:

- Less than 3 months of follow up from the CDK4/6i start to the date of data cut-off;
- Have received CDK4/6i as monotherapy;
- Have received CDK4/6i as adjuvant treatment for localized disease.

Data collection

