Digitalized pathology slide: hematoxylin and eosin (HE) slides coming from diagnostic biopsy or surgical specimens will be digitalized and collected in a pre-defined folder. Both slides from primary tumor and from metastatic sites that underwent biopsy assessment will be collected, if available. If more than one metastatic biopsy has been performed during the course of patient's disease, all the HE slides should be collected, if available. If a patient did not undergo neoadjuvant treatment, diagnostic biopsy of the breast or surgical tumor slide could be collected equivalently; otherwise, the diagnostic biopsy performed before treatment initiation should be taken.

(4) Translational sub-study

Objectives and endpoints of the sub-study

Primary objective:

- To find the mutational status of a gene, or a subset of genes, associated with differential survival outcomes (rwPFS, TTNT-D, TTC-D and OS) of HR+/HER2- aBC patients treated with first-line ET+CDK4/6i;
- To find transcriptomic differential gene expression, or differential expressed pathways, associated with differential survival outcomes (rwPFS, TTNT-D, TTC-D and OS) of HR+/HER2- aBC treated with first-line ET+CDK4/6i.

Secondary objectives:

- To test the effect of PAM50 intrinsic subtype on survival outcomes (rwPFS, TTNT-D, TTC-D and OS) of HR+/HER2- aBC patients treated with first-line ET+CDK4/6i;
- To combine genomics and transcriptomics features with clinical data and radiomics and pathomics features, to build a model able to predict prognosis of HR+/HER2- aBC patients treated with first-line ET+CDK4/6i;
- To test the association between agnostic features included in radiomics model and transcriptomic pathways and mutational status.

Study Population

The same inclusion and exclusion criteria adopted for the RWD sub-study will be adopted for the present sub-study, for the only exception of the following inclusion criterion:

Availability of adequate tumor sample (see Data Collection below) from biopsy of metastatic sites and/or from primary tumor biopsy and/or from surgery specimen.

Data collection

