variants, and copy number variations (CNVs), including both copy number gains and losses, across ~500 genes. The panel will include, but will not be limited to, genes involved in DNA repair systems (e.g. *BRCA1*, *BRCA2*, *PALB2*, *CHEK2*, *ATM*), PIK3CA pathway (e.g. *PIK3CA*, *AKT1*, *PTEN*), estrogen receptor (e.g. *ESR1*). It also allows the quantitative evaluation of tumor mutational burden (TMB) and the analysis of the microsatellite instability (MSI) status.⁹⁷

Transcriptomic analyses

After cellular RNA extraction, RNA quality check and preparation of libraries, RNA will be sequenced with NovaSeq 6000 System. Counts will be analyzed to dissect differential gene expression both at single gene level – through differential gene expression analysis (i.e, Deseq2 method) – and at pathway level – through Gene Set Enrichment Analysis (GSEA), Over Representation Analyses (ORA) and Gene Set Variation Analysis (GSVA).(30,31) The pathway-level analysis will be carried out using the Bioconductor packages fgsea, gsva, and clusterprofiler, taking advantage of HALLMARK, KEGG, and REACTOME gene sets available from GSEA Molecular Signatures Database (http://www.gsea-msigdb.org/gsea/msigdb/collections. jsp). Intrinsic subtypes will be assessed through Absolute Intrinsic Molecular Subtyping (AIMS) algorithm. ^{98–100}

Study duration

Patient enrollment and data collection will start upon approval of the study protocol by the competent ethics committee. All consecutive HR+/HER2- aBC patients treated with first-line ET plus CDK 4/6 inhibitors as per clinical practice in the time interval between January 2016 and December 2030 will be enrolled. The collection and the update of clinical data, medical images and biological samples will continue for an expected duration of 10 years from the enrollment of the last patient. The clinical data, medical images and data obtained from the biological samples will be retained for further 10 years after the end of the study, while the biological samples will be returned to the pathology departments of the Center of origin at the end of the analyses foreseen in the protocol.

Ethical considerations

This study will be conducted according to the Declaration of Helsinki and in compliance with ethical principles regarding human research.

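### DESeq2 is the only gene-level method named for a primary objective on censored survival outcomes, and the protocol does not say how survival enters it

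*Protocol*

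**What the plan says.** In the Protocol, section (4) Translational sub-study, one of the two primary objectives is: "To find transcriptomic differential gene expression, or differential expressed pathways, associated with differential survival outcomes (rwPFS, TTNT-D, TTC-D and OS". These are four time-to-event endpoints. On patients still under treatment, Clinical data collection and management says that "these patients will be censored for the events of interest (e.g. progression, death) if these events have not occurred yet".

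The method is in Biological analyses methodology, Transcriptomic analyses. Genes are analysed singly "through differential gene expression analysis (i.e, Deseq2 method", and pathways "through Gene Set Enrichment Analysis (GSEA), Over Representation Analyses (ORA) and Gene Set Variation Analysis (GSVA". The first is introduced by *i.e.*, so DESeq2 is the method and not one example among several. The section does not say what is contrasted, at what horizon, or what happens to censored patients.

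Two other places bear on the reading. Statistical methods names Kaplan-Meier and Cox regression for survival outcomes in general, without linking them to expression data. Section (3) Medical imaging sub-study plans a classification into early and late progressors, and Radiomics Methodology screens features between two outcome groups that it does not define. Statistical design states that no sample-size calculation was made for sub-studies 2 to 5.

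**The concern.** DESeq2 is a negative-binomial regression in which the gene count is the response and the design variables must be known for every patient. A censored time is not known for every patient, so the stated method does not fit the stated objective without a further step that the Protocol does not give.

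The step most analysts would take, and the one the Protocol takes for imaging, is to sort patients into good and poor outcome groups. Two things are then at stake. Grouping discards information on time, so fewer truly prognostic genes are found. Some groupings also make membership depend on how long ago treatment started, so a gene whose measured level drifts with calendar time (block age, sequencing batch) can look prognostic. The gene list is a primary result of the sub-study, and any pathway analysis that ranks or selects genes from it inherits the problem.

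**Working it through.** The Protocol gives no figure for sub-study 4, so there is none to reproduce. The size was assessed by simulation.

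**Inputs from the Protocol**
- Minimum follow-up of 3 months. The RWD sub-study, whose criteria sub-study 4 adopts, excludes "Less than 3 months of follow up from the CDK4/6i start to the date of data cut-off".
- Enrolment "in the time interval between January 2017 and December 2030 will be enrolled retrospectively and prospectively". Study duration gives January 2016 instead.
- First cut-off: "approximately 2000 patients will be included at the first data cut-off of 1st January 2024". January 2017 to January 2024 is 84 months, so follow-up then runs from 3 to 84 months.
- Medians from the background on HER2 status: OS "mOS: 48.7 vs 58.3 months; p=0.029", PFS 23.6 and 32.3 months. Values between these were used: 53 months for OS, 28 for rwPFS.

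**Assumptions**: 300 patients with RNA, exponential survival, uniform entry, hazard ratio (HR) per SD of expression of 1.25 or 1.28, two-sided 0.05.

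**Event fraction.** With λ = ln 2 / median and follow-up uniform on (a, b), P(event) = 1 − (e^(−aλ) − e^(−bλ)) / ((b − a)λ).
- OS: λ = 0.01308; 1 − (0.9615 − 0.3333)/1.0593 = 0.41.
- rwPFS: λ = 0.02476; 1 − (0.9284 − 0.1250)/2.0052 = 0.60.

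**Closed-form check of the Cox column.** Power ≈ Φ(√events × ln HR − 1.96).
- OS, HR 1.25: events 300 × 0.407 = 122; 11.05 × 0.2231 − 1.96 = 0.51, power 0.69.
- rwPFS, HR 1.28: events 300 × 0.599 = 180; 13.41 × 0.2469 − 1.96 = 1.35, power 0.91.

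Both agree with the simulation.

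**Power, expression unrelated to start date**

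| Endpoint | Group test, HR per SD | Cox | Event yes/no | Median split of observed time | Fixed horizon |
|---|---|---|---|---|---|
| OS | t-test, 1.25 | 0.69 | 0.59 | 0.28 | 0.46 (24 months) |
| OS | t-test, 1.28 | 0.77 | 0.69 | 0.32 | 0.54-0.55 (24 months) |
| OS | negative-binomial Wald, 1.25 | 0.67 | 0.54 | 0.26 | 0.41 (24 months) |
| rwPFS | t-test, 1.25 | 0.83 | 0.65 | 0.44 | 0.48 (12 months) |
| rwPFS | t-test, 1.28 | 0.91 | 0.74 | 0.52 | 0.72-0.73 (24 months) |
| rwPFS | negative-binomial Wald, 1.25 | 0.80 | 0.60 | 0.44 | 0.43 (12 months) |

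The t-test on log expression stands in for the DESeq2 test. The negative-binomial rows (dispersion 0.5, taken as known) show that this stand-in does not drive the result. At p < 0.001, nearer to what a genome-wide search needs, OS power at HR 1.28 is 0.29 for Cox and 0.03-0.19 for the groupings.

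**False positives, gene with no effect on hazard**
- No correlation with start date: about 4-6% for every method.
- Correlation 0.2-0.3 with time since treatment start:
  - Cox: 4-6%.
  - Event yes/no: 31-65% (rwPFS), 20-47% (OS).
  - Median split: 20-43% (rwPFS), 38-76% (OS).
  - Fixed horizon: about 5-11%. With 600 patients and correlation 0.3 this becomes 11-17%.

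**A route without groups.** Entering the null-model martingale residual as a numeric covariate gave power of 0.76 against 0.77 for Cox (OS) and 0.91 against 0.91 (rwPFS) at HR 1.28, with error rates of 0.04-0.06.

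**Later analysis.** Data collection continues for 10 years after the last enrolment, so follow-up could eventually run from 120 to 120 + 168 = 288 months. The event-fraction formula then gives censoring of (0.2082 − 0.0231)/2.197 = 8% for OS and (0.0513 − 0.0008)/4.159 = 1% for rwPFS. At correlation 0.3, false positives for the median split and fixed horizon fall to about 5%. Power is still lost: a median split on OS has 76% against 95% for Cox.

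**The case against.** The strongest reply is that the Protocol never says it will group patients. DESeq2 accepts numeric covariates, so naming it does not force a cut. All three groupings above are inferences. How outcome enters a model is often left to an analysis plan, which is not at hand here. Statistical methods already promises Cox regression for survival outcomes. The biological methods section may describe only assay and bioinformatics: the genomic half of the same primary objective has no association test there either. GSVA scores are per patient and could enter a Cox model.

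Much of this stands. A reader might infer that patients must be cut into groups; the martingale-residual result shows otherwise. A reader might also infer that follow-up length will pass as prognosis. That needs a drift of expression with start date, for which the Protocol gives no figure. It also depends on the grouping chosen, is small with a fixed horizon at 300 patients, and largely vanishes with long follow-up. Event-status groups for OS would keep some of it, since about 8% of patients remain censored. No date is given for the transcriptomic analysis. Drift is plausible, because the material is archived paraffin tissue sent when the analyses are run and no batch or block-age adjustment is mentioned, but it is not established.

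The reply does not reach the mismatch. The section names a specific gene-level method for a specific primary objective, and that method cannot take the endpoint as it is. The general Cox sentence is not tied to expression.

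**Conclusion.** The point holds as a poorly fitting stated method, and the Protocol should be changed. It is not a demonstrated error in results. The firm part is the mismatch between DESeq2 and four censored endpoints, together with the loss of power if outcome groups are used: OS 0.26-0.69 against 0.67-0.77 with Cox, and rwPFS 0.43-0.74 against 0.80-0.91. Every grouping examined found fewer true genes than Cox when expression was unrelated to start date.

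The conditional part is false positives. They rise well above 5% only with an assumed correlation of 0.2-0.3 between expression and start date, with groups formed by event status or observed time, and while follow-up is still short.

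The figures rest on an assumed sample size, effect size, exponential survival and the follow-up pattern at the first cut-off. Cox holds its error rate here because hazard was simulated independent of calendar time. If case mix shifts both expression and hazard, an unadjusted Cox test would be biased too, so the remedy needs adjustment.

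**What to change.** In Transcriptomic analyses, make the primary gene-level test a per-gene Cox regression of each survival endpoint on normalised (variance-stabilised) expression. Adjust for the clinical covariates and for sequencing batch or treatment start year, and control the false-discovery rate across genes. Rank genes for the pathway step by the Cox statistic. Keep DESeq2 for contrasts between groups known at baseline, such as intrinsic subtype or mutation status.

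The cost is a few sentences of text and slightly more analysis work. Samples and data collection do not change.
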